| Standard care team members for both SMA models | Health Educator (RN, RD, or CDE) | Group DSME/SMS instructor | Deliver TTIM self-management education |
| | Medical Provider (MD, NP, or PA) | Medical management | Prescribing provider attends during the last 20 minutes of each group to permit reimbursement. |
| | SMA Coordinator | Coordination and scheduling of TTIM sessions, care team members, and patients | Pre- and post-visit data collection by telephone Schedule patients for group visits Coordinate sessions and schedule BHP involvement (Patient-driven SMAs only) |
| Additional care team members for patient-driven SMAs | Behavioral Health Provider | Instruction and Q&A for mental health SMA topics | Co-lead instruction on mental/behavioral health topics and open-ended discussion/question and answer |
| | Diabetes Peer Mentor (CHW, lay person, patient navigator) | Co-instructor Peer mentoring | Co-lead instruction with HE/BHP (topic based) Share personal experience in group context 1x1 support outside group visit |

C.4.3.1c Aim 1c. Implement patient-driven and standardized diabetes SMAs in 20 primary care practices

In Aim 1c, 20 practices will be randomly assigned to either patient-driven or standardized SMA using covariate constrained randomization and then will implement SMAs, supported by technical assistance from the practice coach. Implementation will be overseen by [name] and managed by the implementation project manager.

Assessment of Practice Characteristics for Covariate Constrained Randomization. Prior to randomization to condition, a representative for each participating practice will complete a brief assessment to collect information that will be used in the covariate constrained randomization (CCR) procedure described below. This information will include patient and practice characteristics that are likely to influence the practice's ability to implement the intervention(s) or be associated with the outcome, such as practice size, practice type (FQHC, private practice), and patient panel characteristics, including race/ethnicity and payer mix (% Medicaid).

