Randomization to Condition. As shown in prior work by [name] (Co-I), covariate constrained randomization will be used to enhance internal validity and achieve balanced study arms.^{55,68,69} The list of practice elements to be collected will be finalized with stakeholders as described above. For randomization, all possible combinations of eligible practices into two groups will be generated using the SAS IML procedure.⁷⁰ For each randomization, a balance criterion, defined

PRINCIPAL INVESTIGATOR (LAST, FIRST, MIDDLE): [name]

as the sum of squared differences on standardized variables between arms will be computed. After examining the distribution of the balance criterion, an optimal set of randomizations will be identified (best 5% to 10%). From this set, one will be chosen using a random number generator, and the practices will be assigned to standardized or patient-driven SMA. We have used these approaches successfully in other studies to achieve well-balanced study arms.⁵⁷

Technical assistance: The practice coach will provide technical assistance to practices as they work to execute plans made for delivering their assigned SMA models. The coach will also monitor progress and ensure accountability to timelines through regular email communication and monthly meetings with the practice team. Each participating practice will identify an **SMA coordinator** (either selected from existing staff or hired for this project) to perform coordination tasks necessary for ensuring fidelity to the research protocol and to ensure practices dedicate sufficient resources and attention to the project. The practice coach has the role of external facilitator, serving as an expert in practice transformation and mentoring the SMA coordinator, who serves as an internal facilitator for local implementation. The SMA coordinator will actively guide all daily aspects of the SMA implementation, and keep site leadership informed of progress or problems in implementation.⁷¹ It is necessary for the SMA coordinator to be an employee of the health care organization in order to recruit patients to participate in interviews, to track participation in SMAs, to coordinate initial and booster training (e.g., upon staff turnover), and to have access to identified data prior to de-identification and transfer to the research team.

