Pilot cohort. At each practice, an initial cohort of patients will be identified and offered either the patient driven SMA or standardized curriculum SMA (based on site randomization). For this initial cohort, the practice coach will meet with the clinical team delivering the intervention or comparator intervention to assist with any potential barriers to delivery, clinical questions, and to garner feedback on the intervention. After each practice has had the initial cohort receive the intervention, any final revisions to the study protocol will be made prior to full “go-live”.

Note on mode of delivery: Following stay at home orders put in place by state and local governments in response to the COVID-19 pandemic in March 2020, our participating primary care sites halted non-emergency in-person visits. The rate of return to in-person visits has varied for our practices based on their location, local levels of risk, and levels of risk deemed appropriate by the clinics themselves. As a pragmatic trial, we consider mode of delivery to be a feature driven primarily by practice decisions about how they will deliver care to their patient population, given their unique needs, preferences, capacity and local context. (Note: This perspective relates to the setting and delivery domains of the PRECIS-2 pragmatic trial planning framework.) As such, delivery of group visits via telehealth, while not a protocol change per se, is specifically allowed as long as practices maintain fidelity to core components (features required to be the same vs different between conditions). Importantly, mode of delivery is not a core component. Practices conducting SMAs via telehealth will document delivery option of groups, report specific issues seen with the telehealth delivery mode. Mode of delivery will be accounted for analytically, consistent with the intent-to-treat analytic framework.

C.4.4.2 Aim 2: Conduct a Cluster Randomized Comparative Effectiveness Trial

C.4.4.2a Recruitment and Retention of Study Participants (PC-2).

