Description of interventions. Both SMA models will consist of 6 in-person 120 minute sessions with TTIM curriculum delivered in a group format with 8 to 10 patients per cohort. Patients will be asked to follow rules of discussion and sign confidentiality agreements at the first session. The care team members, roles, and responsibilities for both standardized and patient-driven SMAs are described in Table 4. Self-management education components for both models address diabetes management challenges as well as mental health comorbidity, particularly depression, as well as problem identification, and personal goal setting (Appendix A). TTIM sessions are manualized and include hand-outs that reinforce the oral materials, tailored to patient health literacy. In both models, patients will be recruited as determined in Aim 1. For instance, the SMA coordinator may invite potential participants to the SMA groups, describe the intervention, collect pre-visit assessment data and schedule the initial SMA session. Assessments will be conducted as described below. The general structure for both SMAs will be:

1. Structured instruction/education on TTIM topics
2. Open discussion and Q&A with SMA instructor(s)
3. Medical management and Q&A with the medical provider (during patient-pull outs or before and after TTIM sessions)
4. Wrap-up and planning for next session

Standardized SMAs. Standardized diabetes SMAs consist of the full TTIM 6-session curriculum, led by HEs, with topics presented in the order listed in Appendix A for all cohorts. The TTIM curriculum used in this study will be slightly adapted to de-emphasize more acute mental health symptoms (such as psychosis) which was provided in the original TTIM program, and slightly increase focus on symptoms of depression and distress as prevalent impediments to diabetes self-management. The SMA coordinator supports patients in making and keeping medical appointments. Medical providers will be present to discuss patient-specific medical questions via one-on-one sessions, either during direct patient pull out or before or after the TTIM sessions, depending on what works best for the practice.

Patient-driven SMAs. For the patient-driven SMAs, the curriculum will be delivered collaboratively by the multidisciplinary care team consisting of several professional providers (HE, medical provider, and BHP) and a lay worker

PRINCIPAL INVESTIGATOR (LAST, FIRST, MIDDLE): [name]

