randomization procedure.⁸⁸ **Covariates (to adjust for potential confounding) and potential moderators will include the following:** mode of delivery of SMA (in-person vs. telehealth), age, gender, race/ethnicity, comorbidity index, insulin dependence, baseline diabetes distress, health literacy, and mental illness. Recent literature on cluster randomized trials notes that imbalance in covariates is more of a problem than for individually randomized trials, and covariates should be included to improve precision and should be selected prior to analysis.^{55,88,89} In the event normality assumptions are not met, we will use transformations to normalize distributions, ordinal or Poisson regression where appropriate, and/or the appropriate link function (e.g. logit link for dichotomized measures).⁹⁰⁻⁹² We will employ intent to treat analyses using general (generalized) linear mixed models (GLMMs) to incorporate data structures that are both hierarchical and longitudinal.^{91,93-97} Hypothesis tests will be two-sided with $\alpha = .05$ or p values reported. Goodness of fit statistics and model fitting diagnostics will be used to assess for influential points, outliers, overdispersion and heteroscedasticity and to evaluate alternative model specifications.⁹⁰ All statistical analyses will be performed using SAS version 9.4 (SAS Institute Inc., Cary, N.C.).

Missing Data (MD-2). Prior to beginning analyses described below to address study hypotheses, we will examine the data carefully to determine whether patterns of missing are ignorable (MCAR or MAR) or non-ignorable (MNAR).⁹⁸⁻¹⁰¹ If so, we will employ likelihood-based methods that utilize all available data (MD-4), adjusting for covariates that are associated with missingness (MD-3). If missingness is non-ignorable we will employ pattern mixture models.¹⁰² Sensitivity analyses will be carried out using multiple imputation approaches (MD-5).

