Quantitative analysis plan. The following analyses will be carried out by [name] and the quantitative analyst. In recent literature on cluster randomized trials, general (or generalized) linear mixed models, adjusted for covariates are recommended for analysis of cluster randomized trials,^{89,103} even after using such procedures as constrained randomization.⁵⁴ Likelihood based models using all available data are the preferred method for analyzing longitudinal data with dropout under MAR conditions.¹⁰⁴⁻¹⁰⁷ This will be our primary analysis; however, we will examine change scores as outcomes, adjusting for baseline, in sensitivity analyses.

To test hypothesis I (comparing patient-centered outcomes): The outcomes for these analyses will be patients' scores on each of these measures at baseline and follow-up (1st and last session). The structure of the data is hierarchical (patients nested within practices) and repeated measures on patients over time. In the basic mixed effects model shown below, Y_{tij} is the score for patient i at time t (baseline: time=0, or follow-up: time=1) in practice j . Intervention is an indicator variable: 0=standard SMA, 1=patient-driven SMA. Covariates will be included in all models but are not shown here for ease of understanding.

$$Y_{tij} = \gamma_{000} + \gamma_{010}(\text{intervention}) + \gamma_{100}(\text{time}) + \gamma_{110}(\text{intervention} \times \text{time}) + u_{00j} + r_{0ij} + \varepsilon_{tij}$$

where γ_{000} represents the initial status for standard SMA; γ_{010} represents the baseline difference between the patient driven SMA practices and standard SMA practices (should be close to 0); γ_{100} is the pre-post change in scores for the standard SMA practices; γ_{110} is the *difference* in pre-post change (i.e. difference in difference) for standard vs. patient-driven SMA practices. r_{tij} is a patient random effect and u_{00j} is a practice random effect, independent of r_{tij} and assumed to have a bivariate normal distribution over practices; ε_{tij} is residual variance. Thus, the intervention effect of patient-driven vs standard SMAs can be tested as $H_0: \gamma_{110}=0$ vs $H_1: \gamma_{110} \neq 0$.

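### Delivery mode is a practice choice made after randomisation; adjusting for it can move the arm effect away from intent-to-treat in hypothesis III, the change-score analysis and any mode-by-time model

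*Combined protocol and SAP*

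**What the plan says.** - **Order of events.** Aim 1c (C.4.3.1c) states that "20 practices will be randomly assigned to either patient-driven or standardized SMA using covariate constrained randomization and then will implement SMAs". Training is separate by arm (C.4.3.1b), and under Technical assistance "The practice coach will provide technical assistance to practices as they work to execute plans made for delivering their assigned SMA models". Practices therefore know their arm while they deliver.
- **Who decides mode.** The note on mode of delivery in the same section says "we consider mode of delivery to be a feature driven primarily by practice decisions". It adds that telehealth is permitted and that mode is not one of the core components.
- **How mode is analysed.** The same note promises that "Mode of delivery will be accounted for analytically, consistent with the intent-to-treat analytic framework". In C4.4.2d.1 the list that serves for both confounder adjustment and moderation starts with "mode of delivery of SMA (in-person vs. telehealth), age, gender, race/ethnicity". The hypothesis I text says "Covariates will be included in all models but are not shown here". The hypothesis III text carries the same covariates over.
- **Other uses of mode.** The section on heterogeneity of treatment effects specifies arm-by-mode and arm-by-time-by-mode models. It also mentions sensitivity analyses on mode, without content. No mode-unadjusted analysis is named.
- **Description of the intervention.** C.4.4.2b states that "Both SMA models will consist of 6 in-person 120 minute sessions", which does not agree with the note permitting telehealth.

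**The concern.** An intent-to-treat contrast compares practices by assigned model, whatever follows from the assignment. Mode is settled after assignment by staff who know the arm, so assignment may influence it. Conditioning on such a variable can do two things. It can remove any part of the arm effect that operates through mode. It can also introduce bias if some practice characteristic drives both the choice of mode and the outcome. Describing the adjustment as consistent with intent-to-treat does not avoid either problem. Every other item in the list is a patient characteristic; mode describes how the intervention was delivered.

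What is at stake is whether the reported arm effects answer the question the trial randomises for. Attendance is the most exposed outcome, since mode could readily affect whether patients come.

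**Working it through.** **1. The plan's own figures.** The power table uses effective n = n / (1 + (m - 1) x ICC). First row: 445 / (1 + 43.5 x 0.03) = 445 / 2.305 = 193.1 (stated 193). The detectable difference at 80% power is (1.960 + 0.842) x sqrt(2 / 193.1) = 0.285 (stated .29). The other five effective sizes also reproduce (140.2, 181.2, 133.9, 76.3, 67.1). No covariate enters these figures, so they do not depend on how mode is handled. The hypothesised effect of 0.30 SD (C.4.1) serves below as the yardstick.

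**2. Printed hypothesis I model.** The test is on γ110, the arm-by-time coefficient. With a baseline and a follow-up score, this is the arm difference in within-patient change. A mode term that is the same at both times cancels from follow-up minus baseline. It can absorb differences in level, but not differences in change.

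**3. Where mode does act.** In a change-score model, with mode-by-time in the repeated-measures model, or with a single outcome on a linear scale:

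- total arm effect = direct effect + (telehealth share, patient-driven minus standardized) x (mode effect)
- mode-adjusted estimate = direct effect

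The documents give neither the shares nor the mode effect. Assume a direct effect of 0.30 SD (positive = favourable), shares of 30% (standardized) and 70% (patient-driven), and a mode effect of -0.2 SD. The total is 0.30 + 0.40 x (-0.2) = 0.22, against an adjusted 0.30: a gap of 0.08 SD. Over share differences of 10 to 40 points and mode effects of 0.1 to 0.3 SD in size, the gap runs from 0.10 x 0.1 = 0.01 to 0.40 x 0.3 = 0.12 SD.

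**4. Simulation.** Assumed: 20 practices, 5 cohorts of 9 patients each, ICC 0.03, 20% missing follow-up, 150 runs per scenario. The repeated-measures models were fitted by generalised least squares with known variance components, and the change-score models by ordinary least squares. The shared cause is an unmeasured practice factor that drives both mode and follow-up score (0.2 SD).

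| Telehealth share, standardized / patient-driven | Mode effect | Shared cause | True total effect | Printed model, no mode | + mode | + mode and mode x time | Change score, no mode | Change score + mode |
|---|---|---|---|---|---|---|---|---|
| 50% / 50% | 0.2 | none | 0.30 | 0.300 | 0.300 | 0.298 | 0.299 | 0.297 |
| 30% / 70% | -0.2 | none | 0.22 | 0.220 | 0.220 | 0.299 | 0.223 | 0.303 |
| 30% / 70% | -0.3 | none | 0.18 | 0.187 | 0.187 | 0.305 | 0.187 | 0.307 |
| 30% / 70% | 0 | 0.2 | 0.30 | 0.292 | 0.292 | 0.206 | 0.296 | 0.209 |
| 50% / 50% | 0 | 0.2 | 0.30 | 0.295 | 0.295 | 0.295 | 0.293 | 0.293 |

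The Monte Carlo standard error is about 0.006, or 0.010 with the shared cause. The two printed-model columns agree to three decimals in every row. The last two mode-adjusted columns move only when the shares differ by arm.

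**5. Hypothesis III.** Acceptance and sessions attended are single outcomes with arm tested directly, so nothing cancels. For sessions attended on a linear scale, step 3 applies. For acceptance on a logit scale it is only approximate. This hypothesis was not simulated.

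**The case against.** The strongest reply is that the primary result is safe. A reader might infer from the covariate list that the DDS-17 effect is no longer the effect of assignment. The printed model does not support that: it tests γ110 and shows no mode-by-time term, and the time-by-mode terms sit in separate additional analyses. This stands. What remains is that the plan does not say whether covariates interact with time. If they do not, the promise to account for mode leaves the primary contrast as it was; if they do, the contrast can shift.

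Second, unconditional inclusion of mode is only one reading. The list covers moderators as well as covariates, it includes baseline distress (already an outcome value in the DDS-17 model), and C4.4.2d.1 screens patient-level covariates at p < .2. This is fair, but mode is not clearly a patient-level covariate. If it were screened, it would be kept when related to outcome, which is when adjustment matters.

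Third, a reader might infer that telehealth use differs by arm, perhaps because the patient-driven model needs several professionals together. No document shows such a difference. C.4.4.2b says the professionals do not overlap, although a peer mentor co-leads every visit. The influences the note gives for the return to in-person visits are location, local risk and the clinic's own view of risk, none of them specific to arm. So dependence of mode on arm is possible but not established.

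Fourth, calendar period may look like a replacement that arm cannot affect. C.4.1 lets practices set their own schedule, so it is not arm-proof either.

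**Conclusion.** The point holds in a limited form. Mode is a post-allocation choice by unblinded practices, it is listed for adjustment, and no mode-unadjusted intent-to-treat analysis is named. The order of events supports this, although the documents give no randomisation dates.

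The printed primary contrast is essentially unaffected. Hypothesis III, the change-score sensitivity analysis and any model with mode-by-time are exposed. Under the assumed 30%/70% split and a mode effect of -0.2 SD, the shift is about 0.08 SD, or 0.08 / 0.30 = 27% of the hypothesised effect. With no mode effect but the assumed shared practice-level cause, a true 0.30 is estimated as about 0.21, so the error can go in either direction. With equal shares in both arms the average shift is nil. The size in this trial cannot be known from the documents.

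**What to change.** - Remove mode from the C4.4.2d.1 adjustment set for the intent-to-treat models, and name the mode-unadjusted models as the intent-to-treat analyses. Adjust only for practice characteristics known before randomisation and for baseline patient covariates.
- State whether covariates enter with time interactions.
- Keep the mode-adjusted, arm-by-mode and arm-by-time-by-mode models under heterogeneity of treatment effects as exploratory. Label mode there as a non-randomised practice choice made after allocation, and report mode by arm.
- If calendar period is used, treat it as a sensitivity adjustment.
- Reconcile the in-person description in C.4.4.2b with the note permitting telehealth.

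The cost is a few sentences. Practices using telehealth already document how groups are delivered, and the power table is unchanged. The one downside is a small loss of precision where mode predicts the outcome.

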For hypotheses I, II and IV, moderator analyses involve inclusion of main effect for time, arm, moderator variable, time x arm, time x moderator, arm x moderator, and time x arm x moderator ***interaction term*** in the model (HT-3). The three-way interaction term tests for differential intervention effectiveness in subgroups identified by the moderator variable. Due to the exploratory nature of these analyses, we do not plan to adjust for multiple comparisons in moderator analyses using the subgroups defined above. However, interpretation of results will include reporting on all subgroup analyses and take into account the number of subgroup analyses performed (HT-4).

Patient cost/time and practice resource/time data analysis. The following analyses will be conducted by [name]. Patient cost/time and practice resource and staff time use data will be examined using simple descriptive measures, including minimum and maximum values (range) and means. Descriptive measures will be calculated for practices in each arm of the study as well as for each type of practice and by level of patient participation. To examine the extent to

PRINCIPAL INVESTIGATOR (LAST, FIRST, MIDDLE): [name]

which practice resources are related to patient participation in SMAs, we will examine multiple values calculated for each measure, including a practice-level value, per-patient that agrees to complete these measures, and the value of the measure per-patient that completes different numbers of sessions. Outlier values of these measures will be confirmed with practices prior to the final analysis of these measures. Results from the analysis of practice resources and staff time use will not involve formal statistical tests of differences, as these data will be used for descriptive rather than comparative purposes.

C4.4.2d.2 Qualitative Analysis

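### The primary model does not say how covariates enter; as main effects they would leave the arm-by-time effect essentially unadjusted for predictors of change

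*Combined protocol and SAP*

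**What the plan says.** The equation for hypothesis I (C4.4.2d.1, quantitative analysis plan) has fixed effects for arm, time and arm-by-time, and random intercepts for practice and patient. The outcome "is the score for patient i at time t (baseline: time=0, or follow-up: time=1) in practice j". The coefficient γ110 "is the *difference* in pre-post change (i.e. difference in difference) for standard vs. patient-driven SMA practices", and the primary test is γ110 = 0. On adjustment the section says: "Covariates will be included in all models but are not shown here for ease of understanding".

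The general quantitative approaches give the reasons for adjusting. The list opens "Covariates (to adjust for potential confounding) and potential moderators will include the following" and names mode of delivery, then "age, gender, race/ethnicity, comorbidity index, insulin dependence, baseline diabetes distress, health literacy, and mental illness". The same paragraph states that imbalance matters more in cluster trials and that "covariates should be included to improve precision and should be selected prior to analysis".

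Time interactions for patient characteristics appear only in the section on heterogeneity of treatment effects: "moderator analyses involve inclusion of main effect for time, arm, moderator variable, time x arm, time x moderator, arm x moderator", followed by the three-way term. The delivery-mode analyses there follow the same pattern.

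Three further statements bear on the point:
- Change scores adjusted for baseline are planned, as a sensitivity analysis.
- The likelihood analysis uses every available observation and adjusts for covariates linked to missingness.
- C.4.1 expects about 15-20% attrition.

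**The concern.** The primary effect is a difference in change. A covariate with one value per patient, entered as a main effect, moves that patient's baseline and follow-up by the same amount and so drops out of the change. The fitted model would look adjusted, because the patient variance falls, while the estimate that is tested hardly moves.

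Imbalance in predictors of change is plausible here. Constrained randomization balances practice features such as size, type, race/ethnicity and payer mix. Patients join after randomization, by accepting an invitation, and hypothesis III predicts that acceptance differs by arm. If the enrolled patients differ between arms on something that predicts how distress changes, the difference goes into γ110 while the report calls the result adjusted.

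**Working it through.** **The plan's own figures.** The documents give no figure for the effect of adjustment on γ110. The power table reproduces without any covariate term. For its first row, effective n = 445 / (1 + 43.5 × .03) = 445 / 2.305 = 193.1 (plan: 193), and detectable d = 2.80 × √(2/193.1) = .285 (plan: .29). The other effective sizes come to 140.2, 181.2, 133.9, 76.3 and 67.1, and all match. The stated power therefore does not rely on covariates improving precision.

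**Algebra.** Add βx for a time-constant covariate x to the hypothesis I model. For a patient with both waves:

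follow-up − baseline = γ100 + γ110 × arm + (difference of the two residuals).

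The term βx cancels, as do both random intercepts. The sum of the two waves contains βx, but it also contains the free baseline arm difference γ010, so it carries no information on γ110. For complete pairs the cancellation is exact.

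If x also shifts change by δ per unit, the arm contrast in change is γ110 + δ × (mean x in the patient-driven arm − mean x in the standardized arm). Without a covariate-by-time term, the bias is δ × imbalance.

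**Simulation with the planned structure.** Assumed inputs: 22 practices × 45 patients (495 per arm), no true arm effect, a binary covariate present in 50% versus 30% that shifts change by 0.4 units, plus one continuous covariate; 40 data sets per scenario, REML fits. Expected bias: 0.4 × 0.20 = 0.08.

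| Data | No covariates | Main effects | Main effects + covariate × time |
|---|---|---|---|
| Complete | 0.082 | 0.082 | 0.003 |
| About 16% dropout | 0.075 | 0.077 | 0.003 |

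In complete data, main effects changed γ110 by 0.000000 and its SE by at most 0.000001. When the covariates did not affect change, they still cut the patient variance from 0.72 to 0.51. The SE depends on the residual variance alone: √(4 × 0.397/495) = 0.0566, which is the fitted value.

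A second simulation had 11 practices per arm, 36 patients each, an imbalance of .25 SD and an effect on change of .30 SD per SD. It gave .074, .074 and .001 with complete data, and .081, .081 and .007 with 18% of follow-up missing.

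**What main effects do under dropout (about 16-18%).**
- Dropout related to covariates in the same way in both arms: γ110 moved by at most 0.0183/0.0611 = 0.30 SE in one scenario and 0.0126/0.0624 = 0.20 SE in the other.
- Dropout related to covariates in opposite directions by arm: it moved by about 0.04 on average (0.04/0.0614 = 0.7 SE) and by at most 0.0590/0.0630 = 0.94 SE.
- The SE changed by under 1% throughout.

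**Baseline distress as a covariate when it is also the time-0 outcome.** With complete data the estimate was unchanged in every data set, so its true sampling error cannot have changed. Yet the patient variance went to 0, the residual variance fell to 0.354, and the model SE became √(4 × 0.354/495) = 0.0535 instead of 0.0566. The drop was 5-7% across scenarios with complete data and 12-13% with dropout (for example 0.0611 to 0.0536, while the empirical SD stayed near 0.060).

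**Range of bias.** From .10 SD × .10 = .01 to .25 SD × .30 = .075. Against the hypothesised .30 this is about 3% to 25%.

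**The case against.** The strongest reply is that the plan never says covariates enter only as time-constant main effects. It calls its equation basic and omits the covariates for readability. That stands: main-effect entry is an inference, supported by the fact that the plan writes out time interactions where it wants them and does so only for moderators.

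A reader might also infer that adjustment does nothing to the primary estimate. The documents do not support that. The analysis keeps patients with baseline only, attrition of 15-20% is expected, and covariates are chosen partly for their link to dropout, which is where main effects can act. Baseline distress, also on the list, is not inert either. Under the non-identity links that the plan allows, exact cancellation would not be expected (not simulated). A rough check for hypothesis II with irregular visits found shifts of up to about a quarter of an SE, but the bias remained.

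A third reply is that the problem is partly handled. Differencing already removes imbalance that affects both waves equally, so only predictors of change matter. The planned change-score analysis would let covariates act on change. Both points are right, but that analysis is a sensitivity analysis and the primary test stays as it is.

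Finally, a reader might take .075 as the expected bias. It is the product of two assumed values. With 36 patients in each of 11 practices per arm, a chance imbalance of .25 SD is 2.1 standard deviations of the between-arm difference at a covariate ICC of .05, and 1.2 at .20, before constrained randomization. It is an unfavourable case, though selection into the groups after randomization is not limited to chance.

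**Conclusion.** The concern holds in a limited form. The plan leaves the form of covariate entry open. On the natural reading, the primary test is exactly unadjusted for patients with both surveys and close to unadjusted overall, unless covariate-dependent dropout differs by arm. The stated aims of controlling confounding and improving precision are then essentially unmet for γ110. The exact cancellation needs only an identity link, time-constant covariates and complete pairs; it does not depend on the simulated values.

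The size of any bias does depend on assumptions: about .01 to .075 over the range shown. The documents do not establish that such an imbalance will occur, and they do not show the stated power to be wrong. Entering baseline distress as a covariate for the distress outcome is a separate fault in the same list, because it makes the model SE too small.

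**What to change.** In the hypothesis I model statement, specify that each prespecified patient-level baseline covariate enters as a main effect and as a covariate-by-time term. For hypothesis II, use covariate by time since baseline. Keep the likelihood analysis of all available data, and report the unadjusted γ110 beside the adjusted one.

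Do not enter baseline distress as a covariate in any model where baseline distress is also an outcome row.

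Keep the baseline-adjusted change analysis, with the same covariates, as a separate sensitivity estimator. It is not equivalent. A difference in differences gives baseline imbalance a weight of 1, whereas the baseline-adjusted model uses the regression slope, and it drops patients without follow-up. In a null simulation of 22 practices × 36 patients the two estimates differed by .037 on average and by up to .14.

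The cost is a few degrees of freedom and no new data. In the simulation with complete data, the time interactions raised the SE from 0.0566 to 0.0578 (about 2%) when the covariates did not predict change, and left it unchanged (0.0579 to 0.0578) when one did. Time interactions for practice-level randomization covariates draw on only 22 practices, so these should be few.
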